### **5.7.2 Subject Replacement Strategy**

Patients who do not complete the intended course of chemotherapy due to reasons other than toxicity will be considered as in-evaluable for the primary endpoint and will be replaced.

[illegible]

Trial Period:	Treatment Cycles a									End of Treatment	Post-Treatment		
Treatment Cycle/Title:	Main Study Screening (Visit 2)	1	2	3	4	5	To be repeated beyond 8 cycles			Discon	Safety Follow-up	Follow Up Visits b	Survival Follow-Up
Scheduling Window (Days):	-28 to -1	± 3	± 3	± 3	± 3	± 3	± 3	± 3	± 3	At time of Discon	30 days post discon ± 7 days	Every 8 weeks post discon	Every 12 weeks
Comprehensive Serum Chemistry Panel	X	X	X	X	X	X	X	X	X	X	X	X	
Fasting triglyceride, cholesterol and glucose	X			X				X					
Urinalysis	X			X				X		X			
T3, FT4 and TSH	X		X			X			X	X	X		
ECG g	X	X	X		X		X g		X g				
Tumor Imaging	X f			X h			X h						
Archival or Newly Obtained Tissue Collection i	X	X											
Correlative Studies Blood Collection j	X	X	X	X						X			

- Treatment cycles are 3 weeks
- Only for patients with ongoing treatment related toxicities
- Pembrolizumab will be given day 1, XL888 twice weekly orally
- ECOG performance status should be done within 10 days or less from day 1 of cycle 1
- Ophthalmologic exam done at baseline and repeated only if there are symptoms
- Baseline imaging with 8 weeks of day 1 is acceptable
- ECG day1 2 to 3 hours after administration of XL888 every other cycle after C2 (C1, C2, C4, C6 etc)
- Scans will be done every 3 cycles between day 15 and day 21
- Paired biopsies will only be obtained from 16 patients on the dose expansion cohort
- Samples will be collected at baseline, day 15, and every cycle for the first 9 weeks. Analysis will include proportion of T, B, NK, memory and effector T cell subsets and expression of PD-1, PD-L1 and B7 family members. Samples will be collected at baseline and on weeks 6 and 9. This will be performed using interferon- gamma and CD107.

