#### **Peripheral blood samples**

Approximately 10 mL of peripheral blood samples will be collected prior to initiation of study therapy, on day 1 of the first 3 cycles. The peripheral blood mononuclear cells will be isolated from these samples and stored in -80°C freezers until analysis. Samples will be evaluated for:

- i. Determine whether there is an increase in expression of T-cell co-stimulatory markers in PBMCs after treatment. Samples will be collected at baseline and every other week for the first 9 weeks. Analysis will include proportion of T, B, NK, memory and effector T cell subsets and expression of PD-1, PD-L1 and B7 family members.
- ii. Determine whether changes in ex vivo functional assays for PBMCs post treatment correlate with response. Samples will be collected at baseline and on weeks 6 and 9. This will be performed using interferon- gamma and CD107.

Shipping and handling instructions

After appropriate processing, the frozen samples will be sent to:

[name] Laboratory  
[name]  
[name]  
Winship Cancer Institute of Emory University  
[name]

Table 5 Laboratory Tests

Hematology	Chemistry	Urinalysis	Other
Hematocrit	Albumin	Blood	Serum $\beta$ -human chorionic gonadotropin†
Hemoglobin	Alkaline phosphatase	Glucose	( $\beta$ -hCG)†
Platelet count	Alanine aminotransferase (ALT)	Protein	PT (INR)
WBC (total and differential)	Aspartate aminotransferase (AST)	Specific gravity	aPTT
Red Blood Cell Count	Lactate dehydrogenase (LDH)	Microscopic exam ( If abnormal )	Total triiodothyronine (T3)
Absolute Neutrophil Count	Carbon Dioxide ‡	results are noted	Free tyroxine (T4)
Absolute Lymphocyte Count	( $CO_2$ or biocarbonate)	Urine pregnancy test †	Thyroid stimulating hormone (TSH)
	Calcium		
	Chloride		Blood for correlative studies
	Glucose		
	Phosphorus		
	Potassium		
	Sodium		
	Magnesium		
	Total Bilirubin		
	Direct Bilirubin ( If total bilirubin is elevated above the upper limit of normal )		
	Total protein		
	Blood Urea Nitrogen		
† Perform on women of childbearing potential only. If urine pregnancy results cannot be confirmed as negative, a serum pregnancy test will be required.			
‡ If considered standard of care in your region.			

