#### **7.1.4.2 Treatment Period**

##### **7.1.4.1 Day 1 ( $\pm 3$ days) of each cycle**

- Record concomitant medications
  - Vitals (temperature, HR, BP and RR)
  - History and physical exam, pill diary (prior cycle see section 11.4) and pill count (prior cycle)
  - ECOG performance status
  - Toxicity assessment
  - 12 lead ECG after XL888 administration in cycle 1, cycle 2 and every other cycle
    - Laboratory Assessments

- Hematology hemoglobin, hematocrit, red blood cell count, white blood cell count with differential and platelet count
  - Chemistry sodium, potassium, chloride, bicarbonate, magnesium, calcium, phosphorus, blood urea nitrogen, creatinine, glucose (random), total bilirubin, LDH, total protein, ALP, ALT, AST, and albumin
  - Tumor markers - when applicable
  - Fasting Lipid profile every 3 cycles starting Cycle 4 (i.e C4D1, C7D1, C10D1, C13D1 etc)
  - Urinalysis every 3 cycles starting Cycle 4 (i.e C4D1, C7D1, C11D1 etc)
    - T3, FT4, TSH cycle 2 and then after every 3 cycle
    - For the cycle 1 day 1 labs, blood samples from the screening tests maybe used if completed within 1 week of day 1
- Blood sample 20 cc for correlative work (only cycle 1, 2, 3)
  - Pembrolizumab 200 mg will be administered as a 30 minute IV infusion every 3 weeks. Given the variability of infusion pumps, a window of -5 minutes and +10 minutes is permitted (i.e., infusion time is 30 minutes: -5 min/+10 min).
- XL888 will be administered orally in the infusion center (first dose of each cycle only) prior to pembrolizumab. **(in selected case in patients receiving paired biopsies XL888 will be held in cycle 1)**

#### 7.1.4.2 Days 4, 8, 11, 15 and 18

- XL888 dose administered and diary completed

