#### 7.1.4.3 Days 8 and 15 ( $\pm 1$ day) in cycle 1 and 2 ONLY

- Record concomitant medications
- Vitals (temperature, HR, BP and RR)
- History and physical exam
- ECOG performance status
- [Toxicity assessment](#)
- Blood for correlative assays on Day 15 of cycle 1
- Laboratory Assessments

- Chemistry sodium, potassium, chloride, bicarbonate, magnesium, calcium, phosphorus, blood urea nitrogen, creatinine, glucose (random), total bilirubin, LDH, total protein, ALP, ALT, AST, and albumin

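### The correlative blood schedules conflict: the week 9 functional-assay sample has no listed draw, and weeks 4 and 8 of the every-other-week series are not scheduled as written

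*Combined protocol and SAP*

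**What the plan says.** The timing of correlative blood is set in several places.

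- Section 7.1.2.7, Peripheral blood samples, opening sentence: about 10 mL, "collected prior to initiation of study therapy, on day 1 of the first 3 cycles".
- Same section, item i (co-stimulatory markers and cell subsets): "Samples will be collected at baseline and every other week for the first 9 weeks".
- Same section, item ii (functional assays against response): "Samples will be collected at baseline and on weeks 6 and 9".
- Section 6.1, flow-chart footnote, for the marker analysis: "Samples will be collected at baseline, day 15, and every cycle for the first 9 weeks". The footnote then repeats weeks 6 and 9 for the functional assays.
- Section 6.1, row "Correlative Studies Blood Collection": marks at screening, cycles 1, 2 and 3, and discontinuation; none at cycle 4.
- Section 7.1.4, Day 1 visits: "Blood sample 20 cc for correlative work (only cycle 1, 2, 3".
- Section 7.1.4, Days 8 and 15 visits (cycles 1 and 2 only): "Blood for correlative assays on Day 15 of cycle 1".
- Section 7.1.4.4, days 15 to 21 of every third cycle: imaging, with no blood listed.
- Section 7.1.4.5, end of treatment: a 20 cc correlative sample.

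The exploratory objective (Section 3.3) is the effect of the combination on the immune profile in blood and tumor. Section 8.3 makes the biomarker analyses descriptive and hypothesis generating.

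**The concern.** The analysis text asks for time points that the operational schedule does not supply. The clearest case is week 9. Both the analysis text and the flow-chart footnote require it, yet the Day 1 list restricts draws to cycles 1 to 3, which excludes the visit where week 9 falls.

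Item ii asks whether functional change tracks response. The first scan falls at days 57 to 63, so week 9 is the planned sample closest to it. Cells not collected and stored at the time cannot be recovered later. Item i has a lesser version of the same problem, because two rules stand side by side for one analysis and the visit lists match only one of them.

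**Working it through.** The plan gives no figure to reproduce. The check is a calendar comparison of the required weeks with the listed draws.

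**Inputs.** Cycle length from the flow-chart footnotes: "Treatment cycles are 3 weeks", so 21 days. Visit windows from Section 7.1.4: ±3 days for Day 1 and ±1 day for Day 15. Listed fixed draws after screening: C1D1, C1D15, C2D1 and C3D1.

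**Study day = (cycle − 1) × 21 + day in cycle.**

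- C1D1: 0 × 21 + 1 = day 1
- C1D15: 0 × 21 + 15 = day 15
- C2D1: 1 × 21 + 1 = day 22
- C3D1: 2 × 21 + 1 = day 43
- First scan, C3D15 to C3D21: 2 × 21 + 15 = day 57, to 2 × 21 + 21 = day 63
- C4D1: 3 × 21 + 1 = day 64

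**Two ways to count weeks.** Elapsed: week w is day 7w + 1. Ordinal: week w is days 7w − 6 to 7w. A draw counts if its visit window touches the required day or days.

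| Week | Needed for | Elapsed day | Listed draw | Ordinal days | Listed draw |
|---|---|---|---|---|---|
| 2 | i | 15 | C1D15 | 8–14 | C1D15 (window reaches day 14) |
| 4 | i | 29 | none | 22–28 | C2D1 (day 22) |
| 6 | i, ii | 43 | C3D1 | 36–42 | C3D1 (window reaches day 40) |
| 8 | i | 57 | none | 50–56 | none |
| 9 | ii | 64 | none | 57–63 | none |

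**Item ii.** Baseline and week 6 are drawn. Week 9 is not, on either count: day 64 is C4D1, which the Day 1 list excludes, and days 57 to 63 carry imaging only. So 1 of 2 post-baseline points has a listed draw. The last fixed draw, day 43, precedes the first scan by 57 − 43 = 14 to 63 − 43 = 20 days. C4D1 would follow the scan by 64 − 63 = 1 to 64 − 57 = 7 days.

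**Item i, read as every other week.** Weeks 2 and 6 are drawn. Week 8 is not. Week 4 is missing on the elapsed count but met by C2D1 on the ordinal count. So 2 of 4 post-baseline points have a draw on the elapsed count and 3 of 4 on the ordinal count.

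**Item i, read by the footnote.** Baseline, day 15 and each cycle match C1D1, C1D15, C2D1 and C3D1, provided that the first 9 weeks means the three cycles that fill them.

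**Volume.** About 10 mL in Section 7.1.2.7, against 20 cc in the Day 1 and end-of-treatment lists: a factor of two.

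**The case against.** The strongest reply is that little is lost. The footnote's rule for the marker analysis largely fits the listed draws, so counting weeks 4 and 8 as missing means preferring the less workable of two texts. Item i asks about change after treatment, and samples at days 15, 22 and 43 can be compared with baseline. Item ii keeps baseline and week 6. The analyses are exploratory and untested.

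Most of this stands. A reader might infer that the every-other-week samples are never drawn, or that the two analyses cannot be done. The documents do not support either: weeks 2 and 6 have listed draws, and both analyses can be run in reduced form.

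A reader might also infer that week 9 would be lost in all 38 to 50 patients. That is not established either. Section 7.1.4 refers sites to the flow chart and to Section 7.1, and both contain the weeks 6 and 9 instruction, so some sites may draw it. A patient who stops on the first scan may have an end-of-treatment sample near week 9, and a patient who stops earlier has no week 9 sample to lose. The documents give no numbers for these groups. Section 4.2.1.2 plans blood T-cell evaluation in all patients but does not mention the functional assays.

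What the reply does not remove is the week 9 conflict. The footnote does not resolve it, because it repeats the week 9 requirement beneath a row with no mark at cycle 4.

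**Conclusion.** The point holds as an inconsistency with a practical consequence. Following the visit lists would leave week 9 undrawn except where an end-of-treatment sample happens to coincide, which removes 1 of the 2 post-baseline functional-assay points. For item i, the every-other-week rule has no listed draw at week 8, nor at week 4 unless weeks are counted ordinally, and it conflicts with the footnote.

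This rests on 21-day cycles and on the visit lists as written. The flow-chart row was read from extracted text, but the conclusion does not depend on it, because the Day 1 list alone restricts draws to cycles 1 to 3. How many patients would be affected cannot be computed from the documents.

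The primary objective, safety and the response endpoints are untouched. The point is still more than clerical, because it determines which samples exist for the exploratory objective. The volume mismatch is minor.

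**What to change.** Use one schedule in Section 7.1.2.7 (opening sentence and items i and ii), the Section 7.1.4 visit lists, and the flow-chart row and footnote. Tie it to existing visits: baseline/C1D1, C1D15, C2D1, C3D1, C4D1 (labelled week 9) and end of treatment. Replace the every-other-week wording in item i with those visits, and state one volume throughout.

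If a C4D1 sample is not wanted, delete week 9 from item ii in both Section 7.1.2.7 and the footnote. The last fixed sample is then 14 to 20 days before the first scan.

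The cost is wording plus, under the first option, one extra research tube at C4D1, a visit that already takes hematology and chemistry.

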### **7.1.3 Other Procedures**

#### **Withdrawal/Discontinuation**

When a subject discontinues/withdraws prior to trial completion, all applicable activities scheduled for the final trial visit should be performed at the time of discontinuation. Any adverse events which are present at the time of discontinuation/withdrawal should be followed in accordance with the safety requirements outlined in Section 7.2 - Assessing and Recording Adverse Events. Subjects who a) attain a CR or b) complete 24 months of treatment with pembrolizumab may discontinue treatment with the option of restarting treatment if they meet the criteria specified in Section 7.1.5.5. After discontinuing treatment following assessment of CR, these subjects should return to the site for a Safety Follow-up Visit (described in Section 7.1.5.3.1) and then proceed to the Follow-Up Period of the study (described in Section 7.1.5.4).

### **7.1.4 Visit Requirements**

Visit requirements are outlined in Section 6.0 - Trial Flow Chart. Specific procedure-related details are provided above in Section 7.1 - Trial Procedures.

#### **7.1.4.1 Screening**

##### **7.1.4.1.1 Screening Period**

All subjects must sign an informed consent document prior to the initiation of any study related procedures. The informed consent document must be signed within 28 days of Cycle 1 Day 1. Screening procedures (with the exception of the scans) are to be conducted within 28 days of Cycle 1 Day 1.

- Review of study eligibility criteria
- Medical History
- Record concomitant medications taken up to 28 days prior to day 1 cycle 1
  - Vitals [temperature, heart rate (HR), blood pressure (BP) and respiratory rate (RR)]
  - Physical Examination, including height and weight
  - Ophthalmologic exam- baseline
  - ECOG Performance Status evaluation (within 10 days or less of cycle 1 day 1)
  - Laboratory Assessments
    - Hematology: hemoglobin, hematocrit, red blood cell count, white blood cell count with differential and platelet count

- Serum chemistry: sodium, potassium, chloride, bicarbonate, magnesium, calcium, phosphorus, blood urea nitrogen, creatinine, total bilirubin, LDH, total protein, ALP, ALT, AST, and albumin. Fasting triglycerides, cholesterol and glucose.
- Serum or urine pregnancy test for women of childbearing potential
- Prothrombin time (PT) and activated partial thromboplastin time (aPTT)
- Urinalysis
- Tumor markers(when applicable such as known elevated tumor markers): CEA, CA19-9, or  $\alpha$ -fetoprotein
- T3, FT4, TSH
- HIV, HBsAg, HCV RNA if clinically indicated
- 12-lead ECG
- Ophthalmologic exam
- Radiologic imaging studies to evaluate tumor status. contrast computed tomography (CT) or magnetic resonance imaging (MRI) of the chest and abdomen and pelvis. Additional imaging may be obtained as clinically indicated. Baseline scans may be done within 8 weeks prior to cycle 1 day 1.
- Baseline fresh biopsy (in selected group) will be obtained with 28 days of day1 cycle 1 and after consent is signed.

#### **7.1.4.2 Treatment Period**

##### **7.1.4.1 Day 1 ( $\pm 3$ days) of each cycle**

- Record concomitant medications
  - Vitals (temperature, HR, BP and RR)
  - History and physical exam, pill diary (prior cycle see section 11.4) and pill count (prior cycle)
  - ECOG performance status
  - Toxicity assessment
  - 12 lead ECG after XL888 administration in cycle 1, cycle 2 and every other cycle
    - Laboratory Assessments

- Hematology hemoglobin, hematocrit, red blood cell count, white blood cell count with differential and platelet count
  - Chemistry sodium, potassium, chloride, bicarbonate, magnesium, calcium, phosphorus, blood urea nitrogen, creatinine, glucose (random), total bilirubin, LDH, total protein, ALP, ALT, AST, and albumin
  - Tumor markers - when applicable
  - Fasting Lipid profile every 3 cycles starting Cycle 4 (i.e C4D1, C7D1, C10D1, C13D1 etc)
  - Urinalysis every 3 cycles starting Cycle 4 (i.e C4D1, C7D1, C11D1 etc)
    - T3, FT4, TSH cycle 2 and then after every 3 cycle
    - For the cycle 1 day 1 labs, blood samples from the screening tests maybe used if completed within 1 week of day 1
- Blood sample 20 cc for correlative work (only cycle 1, 2, 3)
  - Pembrolizumab 200 mg will be administered as a 30 minute IV infusion every 3 weeks. Given the variability of infusion pumps, a window of -5 minutes and +10 minutes is permitted (i.e., infusion time is 30 minutes: -5 min/+10 min).
- XL888 will be administered orally in the infusion center (first dose of each cycle only) prior to pembrolizumab. **(in selected case in patients receiving paired biopsies XL888 will be held in cycle 1)**

#### 7.1.4.2 Days 4, 8, 11, 15 and 18

- XL888 dose administered and diary completed

#### 7.1.4.3 Days 8 and 15 ( $\pm 1$ day) in cycle 1 and 2 ONLY

- Record concomitant medications
- Vitals (temperature, HR, BP and RR)
- History and physical exam
- ECOG performance status
- [Toxicity assessment](#)
- Blood for correlative assays on Day 15 of cycle 1
- Laboratory Assessments

- Chemistry sodium, potassium, chloride, bicarbonate, magnesium, calcium, phosphorus, blood urea nitrogen, creatinine, glucose (random), total bilirubin, LDH, total protein, ALP, ALT, AST, and albumin

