**Dose level 3 will only be tested if we observe 2 DLT's on dose level 2.**

### 5.2.2 Dose Escalation

Starting dose of 45mg; if  $\geq 2$  patients with DLTs in 3 ( $\geq 2/3$ ) or 6 ( $\geq 2/6$ ) subjects; stop and consider reduced dose of XL888. If not, increase dose to 90 mg and test 3-6 patients. If  $\geq 2$  patients with DLTs in 3 or 6 subjects, reduce dose to 60 mg and try again. If an acceptable dose is identified, treat 16 more patients at the MTD. Prior to dose escalation, we will obtain approval from the Data Safety and Monitoring Committee (DSMC).

**5.2.3 Dose limiting toxicity (DLT)** will be defined as any of the following definitely treatment related adverse events during the first 21 days of therapy:

- Grade IV neutropenia lasting more than 8 days; any neutropenic fever or sepsis;
- Grade III with clinically significant bleeding or any grade IV thrombocytopenia;
- Grade III nausea, vomiting, or diarrhea, lasting  $>72$  hours despite adequate supportive care;
- Other non-hematologic treatment-related toxicity at Grade III or higher
- Grade 4 asymptomatic laboratory abnormalities that last for more than 24 hours or Grade 3 asymptomatic laboratory abnormalities lasting more than 21 days is a DLT.
- Grade IV or higher diarrhea, nausea, vomiting
- In ability to take more than 75% of XL888 due to toxicity.

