### 5.3.2 XL888

The following guidelines are provided for the modification of the dose of XL888 in the event of toxicities attributed by the investigator to this study drug. Toxicities unrelated to XL888 will not ordinarily result in the modification of dose. AEs will be defined based on the National Cancer Institute (NCI) Common Terminology Criteria for Adverse Events (CTCAE) version 4.

In general, subjects experiencing **Grade 1 and 2** drug related toxicities should not have the dose of XL888 modified. However, appropriate supportive care should be provided for the management of drug related toxicities. Grade 2 toxicities may require dose or schedule modifications (delaying or omitting individual doses) due to potentially greater clinical significance; however, this should occur after discussion with study PI. .

Dosing of XL888 must be delayed if a subject experiences a **Grade 3 non-hematologic** toxicity. If the toxicity resolves (returned to baseline or decreased to Grade  $\leq 1$ ) within 14 days, dosing of XL888 may be resumed one lower dose level (See section 5.3.2.1). Exceptions to this rule are as follows:

- Grade 3 fatigue: dose modification are left to the PI's discretion;
- Grade 3 nausea, vomiting and diarrhea: dose modification only after optimal prophylactic measures have failed to control the symptoms adequately;

In the case of Grade 4 **non-hematologic** toxicity, **or persistent Grade 3** toxicity despite one dose level reduction, XL888 will be discontinued.

No dose adjustment of XL888 will be performed for anemia.

No dose adjustment for XL888 will be performed for grade 1, 2, or 3 neutropenia or grade 1, 2, or 3(without bleeding) thrombocytopenia.

Dosing of XL888 will be delayed if subjects develop grade 4 neutropenia or grade 3 thrombocytopenia complicated by bleeding or grade 4 thrombocytopenia. If the toxicity resolves (returned to baseline or decreased to Grade  $\leq 1$ ) within 14 days, dosing of XL888 may be resumed one lower dose level (See section 5.3.2.1).

Dose escalation back to the starting dose will not be allowed.

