### **5.3.3 Timing of Dose Administration**

Trial treatment should be administered on Day 1 of each cycle after all procedures/assessments have been completed as detailed on the Trial Flow Chart (Section 6.0). Trial treatment may be administered up to 3 days before or after the scheduled Day 1 of each cycle due to administrative reasons.

All trial treatments will be administered on an outpatient basis.

**Pembrolizumab** 200 mg will be administered as a 30 minute IV infusion every 3 weeks. Given the variability of infusion pumps, a window of -5 minutes and +10 minutes is permitted (i.e., infusion time is 30 minutes: -5 min/+10 min).

The Pharmacy Manual contains specific instructions for the preparation of the pembrolizumab infusion fluid and administration of infusion solution.

**XL888** will be administered twice weekly (days 1 and 4) orally starting on day 1 of every 3-week cycle.

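### Section 7.1.4 schedules no blood count between Cycle 1 Day 1 and Cycle 2 Day 1, so asymptomatic count-based DLTs normally have no scheduled post-dose measurement in the 21-day window

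*Combined protocol and SAP*

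**What the plan says.** **Visit schedule.** Under Treatment Period, the Day 1 list for each cycle includes "Hematology hemoglobin, hematocrit, red blood cell count, white blood cell count with differential and platelet count". The screening list (7.1.4.1) and the end-of-treatment list (7.1.4.5) also include hematology. The Day 8 and Day 15 list for cycles 1 and 2 (7.1.4.3) gives only "Chemistry sodium, potassium, chloride, bicarbonate, magnesium, calcium, phosphorus, blood urea nitrogen, creatinine, glucose (random), total bilirubin, LDH, total protein, ALP, ALT, AST, and albumin" under laboratory assessments. The Day 15 blood draw for correlative assays in cycle 1 is a research sample, not a blood count.

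**Timing.** The Day 1 list states: "For the cycle 1 day 1 labs, blood samples from the screening tests maybe used if completed within 1 week of day 1". Section 5.3.3 states: "Trial treatment may be administered up to 3 days before or after the scheduled Day 1 of each cycle due to administrative reasons". XL888 is also taken on "Days 4, 8, 11, 15 and 18" of each cycle.

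**DLTs.** Section 5.2.3 uses the first 21 days and includes "Grade IV neutropenia lasting more than 8 days; any neutropenic fever or sepsis" and "Grade III with clinically significant bleeding or any grade IV thrombocytopenia". Section 2.0 defines the MTD by DLTs in the first 4 weeks.

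**Hold rule.** Section 5.3.2 states: "Dosing of XL888 will be delayed if subjects develop grade 4 neutropenia or grade 3 thrombocytopenia complicated by bleeding or grade 4 thrombocytopenia". This rule is not limited to cycle 1.

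**Flow chart (Section 6.1).** The first part is illegible in the copy reviewed. The surviving columns are by cycle, with none for Day 8 or Day 15, and the surviving footnotes add no blood count.

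**The concern.** Two of the hematologic DLT limbs can be met by a laboratory value alone: Grade IV thrombocytopenia, and Grade IV neutropenia of sufficient duration. The visit schedule supplies no count during the period in which they are to be judged. A fall in counts that causes no symptoms and recovers before the next Day 1 would leave no record unless someone ordered an extra test.

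The recommended phase 2 dose is the primary objective, and under Section 5.2.2 it turns on single events. Two DLTs in six patients stop escalation at 45 mg or send the 90 mg level down to 60 mg, and one in six does neither. One unseen DLT that turns 2/6 into 1/6 therefore reverses the decision. The DSMC approval step (10.5) sees only the data collected, and Section 8.2 sets no stopping rule behind it. The within-cycle use of the XL888 delay rule has the same gap, because five doses fall between the two scheduled counts.

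**Working it through.** The plan gives no figure to reproduce here. The check sets the scheduled count days against the DLT windows.

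**1. Scheduled count days.** The Day 1 count comes before dosing (5.3.3 puts treatment after that day's procedures), so it cannot show a treatment effect. Cycle 2 Day 1 is 1 + 21 = Day 22, or Days 19 to 25 with the ±3-day window.

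- Nominal gap between counts: 22 − 1 = 21 days.
- Shortest: 19 − 1 = 18 days.
- Longest, with a screening sample 7 days before Day 1 and Cycle 2 starting 3 days late: 25 − (1 − 7) = 31 days.

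**2. Post-dose counts inside the window.**

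- Days 2 to 21 (5.2.3): none nominally; one if Cycle 2 Day 1 falls on Day 19, 20 or 21.
- Days 2 to 28 (2.0): one.

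**3. The duration criterion.** Showing that a Grade IV value lasted more than 8 days takes serial post-dose counts. Either window contains at most one, so scheduled counts cannot establish it.

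**4. Which asymptomatic episodes would be seen.** Take an episode starting on any of Days 2 to 21 (20 start days) and lasting L days, so that it covers days s to s + L − 1. It is seen if a count falls in that span. The lengths are assumptions, and the table enumerates start days; it does not give probabilities. For a count on Day 22, the start days that work run from 23 − L to 21, which is L − 1 of them (for L = 9: Days 14 to 21, or 8).

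| Episode length (days) | As written, by Day 21 | As written, by Day 22 | Cycle 2 Day 1 on Day 19 | Counts added on Days 8 and 15, by Day 21 | Same, by Day 22 | Same, hit by two counts |
|---|---|---|---|---|---|---|
| 3 | 0/20 | 2/20 | 3/20 | 6/20 | 8/20 | 0/20 |
| 5 | 0/20 | 4/20 | 5/20 | 10/20 | 14/20 | 0/20 |
| 7 | 0/20 | 6/20 | 7/20 | 14/20 | 20/20 | 0/20 |
| 9 | 0/20 | 8/20 | 9/20 | 14/20 | 20/20 | 4/20 |
| 12 | 0/20 | 11/20 | 12/20 | 14/20 | 20/20 | 10/20 |

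Under the schedule as written, no episode length is hit by two counts.

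**5. What added counts do and do not solve.** With counts on Days 8 and 15, every episode of 7 days or more is seen by Day 22. A 9-day episode is hit twice for only 4 of 20 start days. Even then, two low values on Days 8 and 15 cover only 15 − 8 + 1 = 8 calendar days, which is not more than 8. Repeat counts after a low value are needed as well.

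**6. XL888 delay rule.** Doses on Days 4, 8, 11, 15 and 18 follow the Day 1 count and precede the next nominal one. The rule can act at each Day 1; no scheduled count feeds it in between.

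**The case against.** A reader might infer that hematologic DLTs cannot be detected at all inside the window. The documents do not support that, for these reasons:

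- Neutropenic fever or sepsis, and Grade III thrombocytopenia with bleeding, present clinically. Days 8 and 15 include history, examination, vital signs and toxicity assessment.
- Section 7.1 allows unscheduled procedures when the investigator judges them clinically necessary.
- Cycle 2 Day 1 can fall on Days 19 to 21, and it always lies inside the 4-week window of Section 2.0.
- The delay rule in 5.3.2 can still be applied to every Day 1 count, so it is not inoperable.

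A second objection is that the background gives no signal of myelosuppression. The adverse events listed at 10% or more in XL888-001 include no cytopenia, and the XL888-specific toxicities in 5.3.2.2 are visual, hepatic, gastrointestinal and QTc. A chemistry panel at Days 8 and 15 fits that profile. This limits how much bias can be claimed. It does not exclude rarer cytopenias or ones specific to the combination, and the plan itself lists count-based DLTs.

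A third is that a hematology line could sit in the illegible part of the flow chart. That cannot be ruled out. However, a row in a chart whose surviving columns are cycles would not by itself place a count on Day 8 or Day 15.

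What remains is narrower. An asymptomatic fall may give nobody a reason to order a count, and the schedule does not supply one.

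**Conclusion.** The point holds in limited form. Following Section 7.1.4 as written, asymptomatic Grade IV thrombocytopenia and prolonged Grade IV neutropenia normally have no scheduled post-dose measurement in the 21-day DLT window. The more-than-8-day criterion cannot be established from scheduled counts under either stated window. Within-cycle use of the XL888 delay rule has no scheduled check.

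Missed events can only lower the DLT count, so the bias is toward under-counting. Its size is unknown because the documents give no cytopenia rate for the combination. It would be wrong to infer that the recommended dose will be mis-selected, or that detection from scheduled counts is always zero: an assumed 9-day episode would be seen on Day 22 for 8 of 20 start days.

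The conclusion rests on the text of Section 7.1.4 and the legible part of the flow chart, and on the nominal 21-day cycle with its ±3-day window.

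**What to change.** - Add the hematology panel already listed for Day 1 to the Day 8 and Day 15 laboratory lists in 7.1.4.3, for cycles 1 and 2.
- State that a Grade 4 count found in the DLT window is followed by repeat counts, so that its duration can be dated.
- Reconcile Sections 2.0 and 5.2.3 on the length of the DLT window. Reconcile 5.2.3, 5.3.2, the Day 1 list, 7.1.4.3 and the flow chart on when counts are taken. Which window governs is for the sponsor to decide.

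The cost is one extra tube at each of two visits per cycle, in cycles 1 and 2, where blood is already drawn for chemistry, plus occasional repeat counts after a low value. Those repeats may need an extra blood draw between visits. No new scheduled visit and no additional patients are needed.
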